10.3.6.1.9. RBC Transfusion

The history of RBC transfusions will be collected.

10.3.6.1.10. SCD-Related Medication Use

Administration of SCD-related medications, such as hydroxyurea, crizanlizumab, L-glutamine, opioids (in daily morphine equivalents), iron chelating agents, ESAs, NSAIDs, folic acid, and penicillin, will be collected.

10.3.6.2. Healthcare Resource Utilization

Data on any outpatient visits (including infusion center, acute care, or telemedicine visit), ED visits, hospitalizations (including total length of stay and time in ICU, if applicable), acute and chronic RBC transfusions, home oxygen supplementation, and renal dialysis will be collected.

10.3.6.3. Health-Related Quality of Life (HRQoL)

Data on HRQoL measures will be collected and completed by the participant electronically. During an event that limits or prevents on-site SOC visits, the HRQoL can be completed remotely if permitted/approved by the IRBs. The questionnaires are provided in [Appendix 2](#).

10.3.6.3.1. Patient Reported Outcome Measurement Information System (PROMIS)

The National Institute of Health self-reported (or caregiver-reported) PROMIS measures of function, symptoms, behaviors, and feelings, will be collected.

If not performed as part of the participant's usual care, standardized PROMIS forms Pediatric-37 v2.0-Profile; Parent Proxy v2.0 Profile-37 and 49 v2.1 Profile will be provided.

10.3.6.3.2. Patient Global Impression of Change (PGIC)

Data from the self-reported Patient Global Impression of Change (PGIC) will be collected. The PGIC is a single question that reflects a participant's or caregiver's belief about the effectiveness of treatment with Oxbryta® (Voxelotor). PGIC is a 7-point scale depicting a participant's rating of overall improvement. Participants/caregivers rate their change as "very much improved," "much improved," "minimally improved," "no change," "minimally worse," "much worse," or "very much worse".

If not performed as part of the participant's usual care, the questionnaire will be provided.

10.3.6.3.3. Numerical Pain Rating Scale (NPRS)

Data from the NPRS will be collected, if it was used to assess acute pain intensity for VOCs and the result was recorded as part of the participant's SOC. Participants will be asked verbally to choose a whole number from 0 to 10 that best describes the severity of pain during the last SCD related vaso-occlusive crisis/pain attack/pain crisis, with 0 being "no pain" and 10 being "the worst pain imaginable."

10.3.6.3.4. Clinical Global Impression of Change (CGIC)

Data from the CGIC will be collected. The CGIC is a brief, stand-alone assessment of the clinician's view of the participant's global functioning prior to and after initiating Oxbryta® (Voxelotol). The CGI provides an overall clinician-determined summary measure that takes into account all available information, including a knowledge of the participant's history, psychosocial circumstances, symptoms, behavior, and the impact of the symptoms on the participant's ability to function. CGIC will be collected, if it does not influence the participant's usual care.

If not performed as part of the participant's usual care, the CGIC will be provided.

10.3.6.3.5. Exercise Tolerance

Any objective measures or reports of exercise tolerance will be collected, if they were recorded as part of the participant's SOC.

10.4. Patient Withdrawal

10.4.1. Discontinuation of Oxbryta® (Voxelotol) and Participant Discontinuation

10.4.1.1. Withdrawal of Consent

Participants and/or their caregiver/legally authorized representative will be informed that participation is voluntary and that they may discontinue Oxbryta® (Voxelotol) treatment or withdraw from the study at any time and for any reason. Any participant who requests to be withdrawn or whose caregiver/legally authorized representative requests withdrawal will be withdrawn from the study by the study doctor.

10.4.1.2. Early Discontinuation of Oxbryta® (Voxelotol)

Participants may be discontinued from Oxbryta® (Voxelotol) treatment by the study doctor or treating physician at any time and for any reason.

Participants who are discontinued or withdraw from Oxbryta® (Voxelotol) treatment will continue to be followed for up to 5 years after the first dose of Oxbryta® (Voxelotol) treatment unless they withdraw consent for study participation.

10.4.1.3. Lost to Follow Up

- A participant will be considered lost to follow-up if he or she repeatedly fails to return for their routine visits per SOC for ≥ 1 year and is unable to be contacted by the study site.
 - A participant who is deemed lost to follow-up and later unexpectedly returns to the site for SOC treatment may be re-consented prior to any new data collection.
 - Any data that was missed during the lost to follow-up period will not be collected.

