4.3. Variables

Variable	Role	Data source(s)	Operational definition
Index date	Study period	Case report form	Inform consent date
Index year	Study period	Case report form	Inform consent date
Pre-Oxbryta	Study period	Case report form	Baseline: any assessments within 12 months before receiving first dose of Oxbryta® (Voxelotor)
Post-Oxbryta	Study period	Case report form	Follow-up period for up to 5 years after the first dose of Oxbryta® (Voxelotor)
End of Treatment	Study period	Case report form	Captured from end of treatment form
End of Study	Study period	Case report form	Captured from end of study form
Age	Demographics	Case report form	Age at first dose of Oxbryta
Sex	Demographics	Case report form	Captured from the inform consent and eligibility form
Race/Ethnicity	Demographics	Case report form	Captured from the inform consent and eligibility form

SCD genotype	SCD disease history	Case report form	Captured from SCD disease history form
Hydroxyurea use	SCD disease history	Case report form	Captured from SCD disease history form
Height	Baseline characteristics	Case report form	Captured from Physical examination form
Weight	Baseline characteristics	Case report form	Captured from Physical examination form
Pre-Oxbryta SCD complications	Medical history	Case report form	Captured from Pre-Oxbryta treatment form
Concomitant Medications	Concomitant Medications	Case report form	Captured from concomitant medications form
Hemoglobin	Effectiveness endpoint measures - Hematology	Case report form	Captured from laboratory assessment-Hematology form
Reticulocyte count (%)	Effectiveness endpoint measures - Hematology	Case report form	Captured from laboratory assessment-Hematology form
Reticulocyte count (absolute)	Effectiveness endpoint measures - Hematology	Case report form	Captured from laboratory assessment-Hematology form
White blood cells (WBC)	Effectiveness endpoint measures - Hematology	Case report form	Captured from laboratory assessment-Hematology form
Aspartate Aminotransferase (AST)	Effectiveness endpoint measures - Hematology	Case report form	Captured from laboratory assessment-Hematology form
Alanine Aminotransferase (ALT)	Effectiveness endpoint measures - Hematology	Case report form	Captured from laboratory assessment-Hematology form
Bilirubin (Total)	Effectiveness endpoint measures - Chemistry	Case report form	Captured from laboratory assessment-Chemistry form

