4.6. Date Imputation

For the partial AE start dates, if month and day are missing, set to June 15. If day is missing, set to 15. If the imputed AE start date is after the AE end date, set AE start date to AE end date. If the AE start date is completely missing, no imputation will be done.

If the end of study date is missing, the last known visit date will be used. If the end of treatment date is partial (month and year is known), the last day of the month is used. If the end of treatment date is partial (only year is known) or is missing completely, the end of the study date is used.

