4.7. Statistical methodology and analyses

The following general analysis will be followed for this study, unless otherwise specified.

Unless otherwise specified, continuous/quantitative variables will be summarized using descriptive statistics which will include the number of participants with data to be summarized (n), mean, standard deviation (SD), median, first and third quartile (Q1, Q3), minimum, maximum, and the number of missing observations. Minimum and maximum will be reported with the same number of decimal places as collected in raw data, while mean, median, Q1, Q3 will be reported with one extra decimal place, and SD will be reported with two extra decimal places. Descriptive statistics for categorical/qualitative variables will be presented with number of participants and percentage (%) of participants in each category.

Percentages will not include the missing category and will be calculated over the number of participants with available (non-missing) data. A category with a zero count will be presented as “0” and a category with a 100 percentage will be displayed as “100”.

The annualized incidence rate is defined as total numbers of a given event for all participants divided by the total patient-year where the total patient-year is defined as the sum of total duration (years) as defined in the Section 4.7.1 for all participants.

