4.7.1. Index date and follow-up

The index date is defined as the inform consent date. The Post Oxbryta period is from the first dose of Oxbryta to the date of end of treatment or end of study.

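### The SAP does not end patient-years at the last observed date for participants lost to follow-up, so post-Oxbryta annualized rates can be biased low

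*Protocol*

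**What the plan says.** Protocol 10.4.1.3 treats a participant as lost who "repeatedly fails to return for their routine visits per SOC for ≥ 1 year and is unable to be contacted by the study site". Someone who "later unexpectedly returns to the site for SOC treatment may be re-consented prior to any new data collection", and for the interval in between, "Any data that was missed during the lost to follow-up period will not be collected".

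SAP 4.7 defines the annualized incidence rate as "total numbers of a given event for all participants divided by the total patient-year" and takes each participant's duration from SAP 4.7.1, which reads: "The Post Oxbryta period is from the first dose of Oxbryta to the date of end of treatment or end of study". It does not say which of the two end dates prevails when both exist, and it subtracts nothing.

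SAP 4.3 gives the source of the end-of-study date as "Captured from end of study form". Neither document says whether a lost participant's form should carry the last contact or the day loss was declared. SAP 4.6 adds: "If the end of study date is missing, the last known visit date will be used". An end-of-treatment date that is wholly missing, or known only to the year, is set to the end-of-study date.

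SAP 4.7.4 defines the post-Oxbryta period differently for safety. It runs through end of study, and the date of dose pausing or treatment discontinuation is used only when the end-of-study date is missing.

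**The concern.** A rate is interpretable only if each unit of time in the denominator is time in which an event could have reached the numerator. The protocol creates stretches for which it says data will not be collected, and the SAP has no rule that takes those stretches out of the patient-years.

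This denominator enters the annualized rates of SCD complications and transfusions (Tables 15.2.6 and 15.2.6.1) and the post-Oxbryta acute pain crisis and VOC rates (SAP 4.7.5, Tables 15.5.1 to 15.5.5). If unobserved time is counted with no events, the post-Oxbryta rate falls, which is the direction that favours the product. The SAP plans no report of unobserved time.

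**Working it through.** **Step 1. What the rules do in each case.** No stated figure can be reproduced: the documents give no event rate, loss fraction or total patient-years.

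| Case | End of the period under SAP 4.6 and 4.7.1 | Unobserved time counted? |
|---|---|---|
| Lost, returns, re-consented | Final end-of-treatment or end-of-study date; one interval from first dose | Yes; no rule removes the gap |
| Never returns, form dated after last contact, end of treatment unknown | The form date | Yes |
| Never returns, form dated at last contact | Last contact | No |
| Never returns, end-of-study date missing | Last known visit | No |
| Never returns, earlier end-of-treatment date known | That date, if it is read as closing the period | Not after that date |

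Under SAP 4.7.4 the last row changes: a recorded end-of-study date takes precedence over an earlier treatment stop.

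**Step 2. Size for a cohort when the time is counted.** Rate as computed ÷ rate over observed time = observed PY ÷ (observed PY + unobserved PY).

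- From the documents: N of about 500 (SAP 4.5; it cancels from the ratio), follow-up of up to 5 years (SAP 4.1), and a threshold of at least 1 year (Protocol 10.4.1.3).
- Assumed: fraction lost f; full follow-up T of 2, 3 or 5 years; lost participants last seen at T/2; gap g = 1 year for every lost participant; no events captured in the gap; similar event rates in lost and retained participants.

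Observed PY = N × [(1 − f) × T + f × T/2]. Unobserved PY = N × f × g.

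Example, T = 5 and f = 10%: observed = 500 × (4.5 + 0.25) = 2,375; unobserved = 500 × 0.10 × 1 = 50; ratio = 2,375/2,425 = 0.979.

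| T (years) | f | Observed PY | Unobserved PY | Ratio | Change in rate |
|---|---|---|---|---|---|
| 2 | 10% | 950 | 50 | 0.950 | −5.0% |
| 2 | 20% | 900 | 100 | 0.900 | −10.0% |
| 3 | 10% | 1,425 | 50 | 0.966 | −3.4% |
| 3 | 20% | 1,350 | 100 | 0.931 | −6.9% |
| 5 | 10% | 2,375 | 50 | 0.979 | −2.1% |
| 5 | 20% | 2,250 | 100 | 0.957 | −4.3% |

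Outside this range, 5% lost with T = 5 gives −1.0%, and 30% lost with T = 2 gives −15.0%. A 2-year gap with T = 5 gives −4.0% at 10% lost and −8.2% at 20%.

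**Step 3. One returner.** With a 5-year window and an assumed uncollected gap of 1.5 years, observed time is 5 − 1.5 = 3.5 years. The rate comes out at 3.5/5 = 0.70 of the rate over observed time.

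**Step 4. With unobserved time removed,** unobserved PY = 0 and the ratio is 1.00.

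**The case against.** The strongest reply is that nothing shows the unobserved time is generally counted. A reader might infer that every lost participant adds an empty year, because loss is declared a year late. The documents do not say that the end-of-study form is dated at the declaration, nor that the end-of-treatment date is usually unknown in lost participants. If the form carries last contact, or is blank, the bias from never-returners is zero. This stands, and it makes that case conditional. It does not dispose of the point: two participants with the same observed data could have denominators a year or more apart, depending only on how a form was dated.

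Returners may be few, since the protocol calls their return unexpected and their re-consent optional. The SAP also does not say whether an end-of-study form filed at loss is superseded on return. The protocol does not say whether the lost period begins at the last visit or at the declaration, so a returner's uncollected gap could be shorter than the whole absence. All of this bears on size. None of it supplies a rule that removes the gap.

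Linked claims (Protocol 10.7.3) could capture some events. But SAP 4.4 says only that secondary sources may be used, SAP 4.3 lists the case report form as the source for complications and transfusions, and Protocol 10.4.1.3 rules out collecting the missed data.

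A reader might also infer that the pre/post comparison must be tilted towards Oxbryta. That is not supported. Pre-Oxbryta history is retrospective, limited to available data and to at most 12 months (Protocol 10.3.3 and Appendix 1). SAP 4.7.5 restricts one VOC analysis to participants with non-missing pre-Oxbryta complications. Incomplete capture there would lower the pre-Oxbryta rate.

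**Conclusion.** The point holds in conditional form and should be corrected. As the SAP is written, a re-consented returner's uncollected gap stays in the patient-years. For a participant who never returns, a year or more of unobserved time is counted as well if the end-of-study form is dated after the last contact and no earlier end-of-treatment date closes the period.

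Where such time is counted, post-Oxbryta annualized rates are biased low. The size cannot be derived from the documents. It is about −2% to −10% under the assumed 10% to 20% lost, a counted 1-year gap and 2 to 5 years of follow-up, and 0% for never-returners whose form carries last contact or is blank. Longer gaps increase it, and loss related to event risk could move the rate either way. The net direction of the pre/post comparison remains open.

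**What to change.** Amend SAP 4.7.1, and make SAP 4.6 and 4.7.4 consistent with it:

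- For participants lost to follow-up, end the post-Oxbryta period at the last visit or contact for which data were collected, whether or not a later end-of-study date is recorded.
- For participants re-consented after loss, remove the time from the last collected visit to the re-consent date from patient-years and from exposure.
- In SAP 4.6, use the same last-collected date when the end-of-treatment date is unknown in a lost participant.
- In SAP 4.7.4, apply the same end date, so that the two definitions of the post-Oxbryta period do not conflict for lost participants.
- Report the number lost, the number who returned, and the unobserved time excluded.

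The cost is a few SAP sentences and minor programming from visit and consent dates already held. The rates may come out slightly less favourable. If sites already enter the last contact date, the change for never-returners only documents that practice.

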10.5. Institutional Review Board (IRB)/Independent Ethics Committee (IEC)

There must be prospective approval of the study protocol, protocol amendments, and other relevant documents (eg, informed consent forms if applicable) from the relevant IRBs/IECs. All correspondence with the IRB/IEC must be retained. Copies of IRB/IEC approvals must be forwarded to Pfizer.

10.6. Ethical Conduct of the Study

The study will be conducted in accordance with legal and regulatory requirements, as well as with scientific purpose, value and rigor and follow generally accepted research practices described in CT24-WI-GL02-RF04.

10.7. Regulatory, Ethical, and Study Oversight Considerations

10.7.1. Regulatory and Ethical Considerations

This study will be conducted in accordance with the protocol and with the following:

- Consensus ethical principles derived from international guidelines including the Declaration of Helsinki and Council for International Organizations of Medical Sciences (CIOMS) International Ethical Guidelines
- Applicable ICH Good Clinical Practice (GCP) Guidelines
- Applicable laws and regulations

The protocol, protocol amendments, ICF, Assent, and other relevant documents (eg, advertisements) must be submitted to an IRB by the study doctor and reviewed and approved by the IRB before the study is initiated.

Any amendments to the protocol will require IRB approval before implementation of changes made to the study design, except for changes necessary to eliminate an immediate hazard to study participants.

Protocols and any substantial amendments to the protocol will require health authority approval prior to initiation except for changes necessary to eliminate an immediate hazard to study participants.

The study doctor will be responsible for the following:

- Providing written summaries of the status of the study to the IRB annually or more frequently in accordance with the IRB requirements
- Notifying the IRB of SAEs or other significant safety findings as required by IRB procedures
- Providing oversight of the conduct of the study at the site and adherence to requirements of 21 CFR, ICH guidelines, the IRB, European regulation 536/2014 for clinical studies (if applicable), European Medical Device Regulation 2017/745 for clinical device research (if applicable), and all other applicable local regulations

10.7.2. Informed Consent and Assent Process

- The study doctor or his/her representative will explain the nature of the study to the participant (or their legally authorized representative) and answer all questions regarding the study.
- Participants must be informed that their participation is voluntary. Participants (or their legally authorized representative) will be required to sign a statement of informed consent that meets the requirements of 21 CFR 50, local regulations, ICH guidelines, Health Insurance Portability, and Accountability Act (HIPAA) requirements, where applicable, and the IRB or study center.
- Participants under 18 years of age (and their parent or legally authorized representative) will review the ICF and sign an Assent Form, according to local IRB guidelines. Participants who initially sign the assent form and subsequently legally become an adult while actively participating in the study (before the end of study) should be re-consented using the adult ICF soon after their status changes.
- The medical record must include a statement that written informed consent was obtained before the participant was enrolled in the study and the date the written consent was obtained. The authorized person obtaining the informed consent must also sign the ICF.
- During an event that limits or prevents on-site SOC visits, the site can obtain consent/assent of a participant remotely, if permitted/approved by the IRBs.
- Participants must be re-consented to the most current version of the ICF(s) during their participation in the study.

- A copy of the signed and dated ICF(s) must be provided to the participant (or their legally authorized representative).

The original copies of the signed and dated ICF (and assent form, if applicable), must be retained in the institution's records and are subject to inspection by representatives of the Sponsor, or representatives from regulatory agencies.

Participants unable to sign the ICF may participate in the study if a legally authorized representative or witness provides the consent (in accordance with the procedures of ICH-GCP and local regulations) and the participant confirms his/her interest in study participation. The participant, parent, or legally authorized representative will be informed that he/she can freely withdraw consent and stop participation in the study at any time with no prejudice to further treatment. It is the parent or legally authorized representative's responsibility to communicate this decision to the study doctor.

In the event of a pregnancy in the female partner of a male participant, a pregnancy consent form will be provided to the partner of the male participant to allow the follow-up of the pregnancy.

10.7.3. Data Protection

- Participants will be assigned a unique identifier by the Sponsor. Any participant records or datasets that are transferred to the Sponsor will contain the identifier only; participant names or any information which would make the participant identifiable will not be transferred.
- The participant must be informed that his/her personal study-related data will be used by the Sponsor in accordance with local data protection law. The level of disclosure must also be explained to the participant who will be required to give consent for their data to be used as described in the informed consent.
- The participant must be informed that his/her medical records and secondary data sources may be examined by study auditors or other authorized personnel appointed by the Sponsor, by appropriate IRB members, and by inspectors from regulatory authorities.
- Linked Pharmacy & Medical Claims Data:
 - By signing the ICF, participants are agreeing to have health records made available as part of the collection of medical and pharmacy claims in order to evaluate concomitant medication and clinical outcomes. This data would be obtained from pharmacy & medical claims databases that have been de-identified and tokenized to match the participant in the study. This de-identified data would be mapped into the project database. Logic checks to confirm accurate linkage would be performed by the clinical monitoring and data management teams.

- All data should be recorded, handled, and stored in a way that allows its accurate reporting, interpretation, and verification. All integrated data would be presented to the site in a 21 CFR Part 11 compliant system for review and clarification of accuracy and quality.
- The investigator/designee is responsible for assuring that all data (whether entered into the eCRF or abstracted from the electronic health records (EHR) is complete, accurate, and that entry and updates are performed in a timely manner. The Investigator must certify that the data entered are complete and accurate.
- After final database lock, the investigator will receive copies of all participant data for archiving at the investigational site.

